10.4 Methods for Evaluation of Pathological Response

The post-treatment pathologic tumor stage will be determined from each patient's cystectomy pathology report according to American Joint Commission on Cancer (AJCC) Staging system T, N, M categories for bladder cancer (Appendix V).

10.5 Pathologic Tumor Response Definitions

10.5.1 Pathologic Response

Pathologic response (<ypT2N0M0) is defined by post-treatment radical cystectomy tumor stages with N0 and M0 status with the following T-stages: T0, Ta, Tis, T1.

10.5.2 Pathologic Complete Response

Pathologic response (ypCR) is defined by post-treatment radical cystectomy tumor stages with N0 and M0 status with the following T-stages: T0.

10.5.3 Pathologic Non-Response

Pathologic non-response (ypNR) is defined by post-treatment radical cystectomy tumor stages with any node-positive (N1, N2, N3) or metastases-positive (M1) status. In addition, patients with N0 and M0 status with the following T-stages are also classified as pathologic non-responders: T2, T2a, T2b, T3, T3a, T3b, T4, T4a, T4b.

10.6 Tumor IHC Staining Intensity Definitions

For validated IHC targets, standardized IHC staining intensity cutoffs will be utilized. For all other IHC targets, IHC staining will be categorized as:

Grade	Stain
0	<1% cells stained
1+	1 to <5% cells stained
2+	5 to 10% cells stained
3+	≥ 10% cells stained

10.7 Recurrence-Free Survival (RFS) as per RECIST 1.1

RFS is defined as the duration of time from start of treatment to time of first documented recurrence (after radical cystectomy) or death, whichever occurs first.

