## **2. INTRODUCTION**

### **2.1. Objective of the Statistical Analysis Plan**

This statistical analysis plan (SAP) describes the planned analysis of the safety and efficacy data from this study. A detailed description of the planned tables, figures and listings (TFLs) to be presented in the Clinical Study Report (CSR) is provided in the accompanying TFL template document.

The intent of this document is to provide guidance for the analysis of data related to safety and efficacy to describe any applicable statistical procedures. In general, the analyses come directly from the protocol, unless they have been modified by agreement between the Sponsor and Quality Data Services, Inc. (QDS). A limited amount of information concerning this study (e.g., objectives, study design) is summarized to help the reader interpret the accompanying TFL templates. That information is not a synopsis of the study and does not require review or approval because it is simply extracted from the protocol. Attached signatures indicate approval of the statistical analysis sections of the SAP, as well as accompanying TFL templates. These sections must be agreed upon prior to database lock. When the SAP and TFL templates are agreed upon and finalized, they will serve as the template for a portion of this study's CSR.

This SAP supersedes the statistical considerations identified in the protocol; where considerations are substantially different, they will be so identified. If additional analyses are required to supplement the planned analyses described in this SAP, they may be performed and will be identified in the appropriate section of the CSR. Any substantial deviations from this SAP will be agreed upon between the sponsor and QDS. Deviations from this SAP, both substantial and non-substantial, will be documented in the CSR. Any updates to their respective analyses, study designs, and TFL presentations after this SAP is finalized and approved will be documented in a running Note to the SAP document.

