### 5.6. Recurrence-Free Survival (RFS) as per RECIST 1.1

Recurrence is defined as the Progressive Disease (PD) in Overall Response assessed by ERECIST 1.1 or death after radical cystectomy. RFS time is defined as the duration of time from start of treatment to time of first documented recurrence (after radical cystectomy) or death, whichever occurs first.

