### **7.7. Efficacy Analysis**

All Efficacy analyses are performed for efficacy population except Recurrent-Free Survival and Overall Survival analyses. The RFS and OS analyses are performed for safety population.

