### **7.7.4. RFS survival analysis in each cohort**

Recurrence-free survival (defined as patients who are alive and without evidence of disease recurrence) from start of treatment to first documented recurrence will be estimated using Kaplan-Meier method for each treatment cohort and compared between the two cohorts using a log-rank test. The two-year recurrence-free survival estimates and confidence intervals will be provided for each cohort. If patients do not have recurrence tumor or death event then they are censored at the last RECIST assessment date.

The proportion of patients with recurrence-free survival at the two-year time point from registration will be displayed for each cohort.

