## **8. SUMMARY OF CHANGES FROM PROTOCOL-SPECIFIED ANALYSES**

No changes are planned.

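### The RFS event rule counts only recurrence after cystectomy or death, so a living patient whose disease progresses and who is never operated on is censored, although the endpoint is survival without disease at 2 years

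*Protocol*

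**What the plan says.** **Restricted to events after surgery.** Protocol 10.7: "RFS is defined as the duration of time from start of treatment to time of first documented recurrence (after radical cystectomy) or death". SAP 5.6, second sentence: "RFS time is defined as the duration of time from start of treatment to time of first documented recurrence (after radical cystectomy) or death".

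**Not restricted.**
- Protocol 13.2.3 (item 4) and SAP 7.4.2.5 list the endpoint as the proportion alive with no disease at 2 years.
- Protocol 13.2.3.1 (item 4) and SAP 7.7.4 describe RFS as being alive without evidence of recurrence, and do not mention cystectomy.
- SAP 7.5.2 applies the word recurrence to objective disease events before the end of treatment. Protocol 10.1 calls these progression.

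**Ambiguous.** SAP 5.6, first sentence: "Recurrence is defined as the Progressive Disease (PD) in Overall Response assessed by ERECIST 1.1 or death after radical cystectomy". The closing phrase about cystectomy may qualify PD and death, or death alone.

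**Who is analysed, and how.** SAP 7.7: "The RFS and OS analyses are performed for safety population". SAP 7.5.1 admits anyone who received one dose; surgery is not needed. SAP 7.7.4 on non-events: "If patients do not have recurrence tumor or death event then they are censored at the last RECIST assessment date". SAP 7.7.4 also plans a separate figure: "The proportion of patients with recurrence-free survival at the two-year time point from registration will be displayed for each cohort".

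**The concern.** Both documents foresee the patient in question. Protocol 8.1 stops therapy for progression, Protocol Section 11 schedules a scan after the second dose and before surgery (footnote 15), and footnote 16 provides for cystectomy not being performed. Under the restricted definition this patient has no route to an RFS event except death. While alive, the patient leaves the risk set as censored.

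That censoring is informative, because it happens to patients whose treatment has failed. The error runs in one direction, towards a higher 2-year RFS. Two programmers working from different sections could also code the same patient as an event or as censored, in both the Kaplan-Meier curve and the separate 2-year proportion. The log-rank comparison between cohorts would inherit whichever choice was made.

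**Working it through.** **Plan's own figure.** There is none to reproduce. Neither document gives an RFS rate, event count, power or sample size, or a rate of progression that leads to no surgery.

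**Reading the rule through for one patient** (dosed, PD on the pre-surgery scan, no cystectomy, alive):
1. In the RFS analysis set? Yes: one dose suffices (SAP 7.5.1, 7.7).
2. Recurrence after cystectomy? No: there was no cystectomy.
3. Death? No.
4. So censored at the last RECIST assessment (SAP 7.7.4).
5. Alive with no disease at 2 years (Protocol 13.2.3, SAP 7.4.2.5)? No.

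Steps 4 and 5 give opposite answers for the same patient.

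**Size, by illustration.** N is the number treated (12 and 24, SAP 7.1). The rest are assumptions: k patients progress and are never operated on, d of these die within 2 years, e later events occur among the other N−k, and follow-up is otherwise complete. Living progressors are censored at progression, before the later events.
- Literal rule: 2-year RFS = (N−k−e)/(N−k+d)
- PD counted as an event: 2-year RFS = (N−k−e)/N

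| Cohort | N | k | e | d | Literal rule | PD as event | Points too high |
|---|---|---|---|---|---|---|---|
| 1 | 12 | 2 | 4 | 0 | 6/10 = 60.0% | 6/12 = 50.0% | 10.0 |
| 1 | 12 | 2 | 4 | 1 | 6/11 = 54.5% | 6/12 = 50.0% | 4.5 |
| 1 | 12 | 2 | 4 | 2 | 6/12 = 50.0% | 6/12 = 50.0% | 0 |
| 1 | 12 | 1 | 4 | 0 | 7/11 = 63.6% | 7/12 = 58.3% | 5.3 |
| 2 | 24 | 3 | 8 | 0 | 13/21 = 61.9% | 13/24 = 54.2% | 7.7 |

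First row in full: censoring 2 of 12 leaves 10 at risk, and four events give 9/10 × 8/9 × 7/8 × 6/7 = 6/10. With the two as events, 10/12 × 6/10 = 6/12.

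With a single such patient alive, varying the later events (2 to 4 in Cohort 1, 4 to 8 in Cohort 2) gives an excess of 5.3 to 6.8 points in Cohort 1 and 2.7 to 3.4 points in Cohort 2.

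**The separate 2-year proportion.** SAP 7.7.4 does not say how these patients are classed. Each one classed as recurrence-free adds 1/12 = 8.3 points in Cohort 1 or 1/24 = 4.2 points in Cohort 2.

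**Against sampling error.** The exact 90% interval for 6/12 is 24.5% to 75.5%, so a 10-point shift lies well inside it.

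**The case against.** The best defence is that the intent is plain. SAP 5.6 starts by equating recurrence with RECIST PD, SAP 7.5.2 uses the word recurrence for events before the end of treatment, and SAP 7.7.4, the operative analysis section, has no cystectomy restriction. On that view a sensible programmer counts the patient as an event. These passages do support that reading, but they do not remove the parenthesis in Protocol 10.7 and SAP 5.6, which are the formal definitions of RFS. If the endpoint wording governs, those definitions are wrong as written. If the definitions govern, the endpoint wording is wrong.

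The limits on size also stand. The counts above are assumed, there is no bias if every such patient dies within 2 years, and RFS carries no power claim or decision rule in this Phase Ib trial.

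A reader might infer two stronger points, and the documents support neither.
- *That the SAP departs from the protocol without saying so.* SAP 2.1 says "This SAP supersedes the statistical considerations identified in the protocol; where considerations are substantially different, they will be so identified", and SAP 8 says "No changes are planned". But SAP 5.6 carries over the wording of Protocol 10.7, so that statement is consistent with it. The conflict lies inside each document.
- *That the Kaplan-Meier excess could reach 16.7 points* (8/12 = 66.7% against 50.0% in the first example). That needs the two progressors to have RECIST assessments beyond 2 years. Protocol Section 11 does not require them: footnote 16 ends study imaging once new therapy starts and asks for continued assessments only in patients removed for reasons other than progression, and the 2-year period in footnote 18 runs from a cystectomy these patients never had. Censoring near progression is the better-supported case.

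**Conclusion.** The concern holds. Within both the protocol and the SAP, the RFS event definition conflicts with the endpoint it is meant to measure. Applied as written to the safety population, it censors living patients who progressed and were never operated on, and biases 2-year RFS upward unless all of them die within 2 years.

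The size cannot be stated from the documents. With 2 such patients alive among 12 and 4 later events, censored at progression, the excess is 10.0 points. The result rests on the assumed counts, on censoring at progression and on otherwise complete follow-up. It is smaller than the sampling error in either cohort, affects a secondary endpoint only and leaves the primary safety endpoint untouched. It should still be corrected, because the error is directional and can be avoided by wording.

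The denominator for pathologic response is a separate matter: it is prespecified in Protocol 10.1 and SAP 7.5.2 and is not part of this finding.

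**What to change.** In Protocol 10.7 and SAP 5.6 and 7.7.4, define the RFS event as the first of:
- RECIST PD in a patient who does not subsequently undergo cystectomy, dated at PD;
- recurrence after cystectomy;
- death from any cause after the first dose.

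PD before a cystectomy that then takes place would not itself be an event, and the text should say so. Defining the first item by the absence of later surgery, not by progression having prevented surgery, avoids the need for a recorded reason. It also covers patients left unoperated for other reasons who progress later.

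Apply the same classing to the Kaplan-Meier curve and to the 2-year proportion in SAP 7.7.4.

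Use one time origin. Protocol 10.7, SAP 5.6 and the Kaplan-Meier analysis in SAP 7.7.4 start at first treatment. Protocol 2.2, 13.2.3 and 13.2.3.1, SAP 7.4.2.5 and the 2-year proportion in SAP 7.7.4 start at registration. The difference is small, since Protocol 4.3 asks for treatment within 10 working days of registration.

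The cost is wording changes in both documents. No new data are needed: Protocol 8.2 already requires dates of progression, first subsequent therapy and survival, and surgery is a scheduled study procedure. Reported RFS may be slightly lower.

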10.8 Overall Survival (OS)

OS is defined as the duration of time from start of treatment to time of death.

11. Study Parameters

1. All pre-study assessments and scans should be done ≤ 4 weeks prior to registration with exception of the most recent TURBT that showed muscularis propria invasion which can be done within 70 days.

Procedures	Screening	TURBT ¹ (if needed)	Infusion 1	Infusion 2*	Surgery	Off Treatment ¹⁶	Follow-Up ¹⁸
			Day 1	Day 1			
Written Informed Consent	X						
Pathology ¹	X ¹	X ¹					
Disease Characteristics ²	X						
Medical/Surgical History	X						
Assessment of Baseline Signs & Symptoms	X						
Height	X						
Physical Exam including Weight	X	X	X	X	X	X	
Vital Signs ³ (Temperature, Pulse, Blood Pressure)	X	X	X	X	X	X	
Performance Status	X	X	X	X	X	X	
CBC/Differential/Platelets ⁴	X	X	X	X	X	X	
Chemistry ⁵	X	X	X	X	X	X	
Hepatitis B & C Testing ⁶	X						
TSH, FT3, FT4 ⁷	X			X	X	X	
Serum Pregnancy Test ⁸	X		X ⁸	X ⁸			
Serum Cortisol Level	X				X		

Procedures	Screening	TURBT ¹ (if needed)	Infusion 1	Infusion 2*	Surgery	Off Treatment ¹⁶	Follow-Up ¹⁸
			Day 1	Day 1			
ECG	X						
Chest/Abdomen/Pelvic CT with or without Contrast or MRI ⁹	X				X ¹⁵		X
Research Blood Specimens ¹⁰	X (Streck DNA tube only)		X	X	X	X	X ¹⁰
Research Urine Specimens ¹⁰			X	X	X	X	X ¹⁰
Research Tissue Specimens ¹¹		X			X		X ¹¹
Treatment Administration ¹²			X	X			
Oxygen Saturation by Pulse Oximetry ¹³			X	X			
Radical Cystectomy with Pelvic Lymph Node Dissection ¹⁴					X		
Concomitant Medication Review	X		X	X	X	X	
Adverse Events Assessment			X	X	X	X ¹⁷	
Survival Status							X

* **Scheduled Visits:** +/-3 day window is allowed for scheduled study therapy, required tests and/or visits except as otherwise noted. Delay due to holidays, weekends, bad weather or other unforeseen circumstances will be permitted.

1 Cystoscopy with TURBT showing muscularis propria should be performed within 10 weeks (56 days) of starting study therapy. Patients must have sufficient baseline tumor tissue from either the initial or repeat TURBTs. **Tumor tissue content for CD8+ T-cell density assessment must be qualified as sufficient (≥ 20% tumor content in the specimen in initial or repeat TURBT with highest tumor content) for analysis and must be documented by the local pathologist prior to registration.** (The actual CD8+ T-analysis does not need to be done by the Central Laboratory prior to registration.) This documentation can occur at any time prior to registration. Patients will complete all other screening studies (i.e. labs, imaging, history, exam, etc.) within 28 days of registration.

2 Record date of diagnosis and stage.

- 3 Patients will have Temperature, Pulse and Blood Pressure taken at each visit. In addition, patients will have their blood pressure and pulse measured before, during and after the infusions at the following times:
 - At the beginning of the infusion
 - After nivolumab infusion and before lirilumab infusion for patients receiving lirilumab
 - At the end of the infusion
- 4 CBC with differential and platelet count which includes WBC, ANC, Platelets, Hemoglobin, and Hematocrit required prior to each dose of study therapy. Results known prior to treatment administration.
- 5 Albumin, BUN/creatinine, uric acid, sodium, potassium, chloride, glucose, calcium, alkaline phosphatase, AST, ALT, total bilirubin, and total protein.
- 6 Hepatitis B surface antigen (HBsAg), and Hepatitis C (HCV) testing within 4 weeks of registration. These tests may be repeated during the course of the study, if clinically indicated.
- 7 TSH, FT3, FT4. Please note this is Free T3 and Free T4.
- 8 Required for sexually active females of child-bearing potential. Infusion 1 and Infusion 2: Must be within 24 hours prior to treatment with nivolumab.
- 9 Chest/ Abdomen/Pelvic CT with or without contrast. CT with contrast is the preferred method unless otherwise contraindicated due to allergy, impaired renal function, etc. MRI exams of the chest and/or abdomen/pelvis may be performed, if CT of chest and/or abdomen/pelvis cannot be obtained. Preferably, use the same modality (CT or MRI) that was initially used during the study course, if possible.
- 10 Research blood and urine samples shall be obtained at time points noted below. Refer to Section 14 for details. **NOTE: Blood draw order is specified in the PrE0807 Lab Manual.**

Screening

One 10 mL Streck DNA tube (for germline)

Before First and Second Neoadjuvant Dose

Peripheral Blood: One 10 mL red top tube, two 10 mL green top tubes, one 10 mL Streck DNA tube and one 10 mL Streck RNA

Urine: At least 30 mL in standard urine cup

Pre-Radical Cystectomy

Peripheral Blood: One 10 mL red top tube, two 10 mL green top tubes, one 10 mL Streck DNA tube and one 10 mL Streck RNA

Urine: At least 30 mL in standard urine cup

Off Treatment Visit (approximately 30 days after Cystectomy)

Peripheral Blood: One 10 mL red top tube and two 10 mL green top tubes, one 10 mL Streck DNA tube and one 10 mL Streck RNA

Urine: At least 30 mL in standard urine cup

At Time of Recurrence, if feasible

Peripheral Blood: One 10 mL red top tube, two 10 mL green top tubes, one 10 mL Streck DNA tube and one 10 mL Streck RNA

Urine: At least 30 mL in standard urine cup

- 11 Research tumor tissue samples shall be obtained at time points noted below. Refer to Section 14 for details.

Screening/Study Entry

FFPE: Up to 3 blocks preferred or 1 H&E slide plus minimum of 20 unstained slides (30 preferred)

Radical Cystectomy

FFPE: Up to 3 blocks preferred or 1 H&E slide plus minimum of 20 unstained slides (30 preferred)

At Time of Recurrence, if feasible

FFPE: Up to 3 blocks preferred or 1 H&E slide plus minimum of 20 unstained slides (30 preferred)

- 12 See Section 6 for Treatment Plan and Section 7 for Dose Delays.

Cohort 1: Nivolumab 480 mg IV over approximately 30 minutes every 4 weeks for 2 neo-adjuvant doses (week 0 and 4) followed by radical cystectomy with bilateral (standard or extended) pelvic lymph node dissection as soon as possible but within 6 weeks after the last neoadjuvant infusion.

Cohort 2: Nivolumab 480 mg IV over approximately 60 minutes every 4 weeks for 2 neo-adjuvant doses (week 0 and 4) with at least a 30 minute rest between infusions followed by lirilumab 240 mg IV over approximately 60 minutes every 4 weeks for 2 neo-adjuvant doses (week 0 and 4) followed by radical cystectomy with bilateral (standard or extended) pelvic lymph node dissection as soon as possible but within 6 weeks after the last neo-adjuvant infusion.

- 13 Record oxygen saturation by pulse oximetry at rest and after exertion at each on-study visit prior to dosing.

- 14 Radical cystectomy with bilateral (standard or extended) pelvic lymph node dissection to be performed as soon as possible but within 6 weeks after the last neoadjuvant infusion.

- 15 Obtain CTs (or MRI as noted above) after second dose of nivolumab +/- lirilumab and before surgery.

- 16 Thirty (30) days +/- 7 days after cystectomy. If patient is removed from treatment for reason(s) other than progression, follow with regular tumor assessments per standard of care until progression or start of new treatment. Once a patient has initiated a new therapy, no further imaging assessments for this study are required.

NOTE: If cystectomy is not performed, Off Treatment visit should be performed at next scheduled appointment or treating physician discretion, as clinically indicated.

- 17 Patients will be followed for adverse events for 100 days after their last dose of neoadjuvant therapy. Adverse events may be reviewed at the next visit \geq 100 days after last dose of neoadjuvant therapy or phone follow-up may be done to review adverse events. However, an adverse event occurring at any time after discontinuation of study therapy that is felt to be at least possibly related to study therapy should be recorded.

- 18 Patients will be followed clinically and radiographically per standard of care (every 3-6 months) at the discretion of the treating physician for at least 2 years post-cystectomy or when study-wide follow-up ends. Date of diagnosis for progression, first subsequent therapy and survival shall be reported. Phone follow-up may also be done for patients unable or unwilling to return for follow-up evaluations.

12. Drug Formulation and Procurement

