8.2 Duration of Follow-Up

Patients will be followed for adverse events for 100 days after their last dose of neoadjuvant treatment. Adverse events may be reviewed at the next visit \geq 100 days after last dose of neoadjuvant therapy or phone follow-up may be done to review adverse events. However, if a patient experiences an adverse event $>$ 100 days after their last dose of study medication that is felt to be, in the opinion of the investigator, possibly, probably or definitely related to study therapy, the adverse event should be reported.

Patients will be followed clinically and radiographically per standard of care (3 -6 months) at the discretion of the treating physician for at least 2 years post-cystectomy or when study-wide follow-up ends. Date of diagnosis for progression, first subsequent therapy and survival shall be reported. Phone follow-up may also be done for patients unable or unwilling to return for follow-up evaluations.

If a patient is removed from treatment for reason(s) other than progression, follow with regular tumor assessments per standard of care until progression or start of new treatment.

For patients who are registered but do not receive any protocol therapy, baseline and follow-up information per Section 11 will be collected.

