8.3 Criteria for Removal from Study Treatment

A genuine effort will be made to determine the reason(s) why a patient fails to return for the necessary visits or is discontinued from the trial, should this occur. It will be documented whether or not each patient completed the clinical study. If for any patient study treatment or observations were discontinued, the reason will be recorded on the appropriate eCRF. Reasons that a patient may discontinue treatment in a clinical study are considered to constitute one of the following:

1. Completion of all study therapy and follow-up.
2. Recurrence of disease or documented progression of disease.
3. Intercurrent illness that prevents further administration of treatment per investigator discretion.
4. Unacceptable adverse events.
5. Investigator and/or patient discontinue study therapy.
6. Pregnancy.

7. Develops a second malignancy (except low risk cervical cancer or cancer in-situ) that requires treatment, which would interfere with this study.
8. The patient may choose to withdraw from the study at any time for any reason.
9. General or specific changes in the patient's condition that render the patient unacceptable for further treatment in the judgment of the investigator.
10. Severe non-compliance to protocol as judged by the investigator.
11. Lost to follow-up.
12. Death.
13. Closure of study by PrECOG.

Any patient who receives at least one dose of nivolumab or lirilumab will be included in the safety analysis. Patients who discontinue study treatment early should be followed for response assessments, if possible. Follow-up will continue per Section 11, as applicable.

9. Adverse Event Reporting

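### The documents conflict on whether tumor assessment continues after new therapy, and the RFS censoring rule can turn that gap into outcome-dependent censoring

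*Protocol*

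**What the plan says.** Two instructions on imaging stand side by side.

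- **Assessment ends at new therapy.** For patients taken off treatment for a reason other than progression, Protocol 8.2 tells sites to "follow with regular tumor assessments per standard of care until progression or start of new treatment". Footnote 16 to the Section 11 schedule gives the same instruction and adds: "Once a patient has initiated a new therapy, no further imaging assessments for this study are required". SAP Appendix I, footnote 16, repeats it.
- **Assessment runs for two years.** Footnote 18 to the same schedule asks for clinical and radiographic follow-up every 3-6 months as standard of care, "for at least 2 years post-cystectomy or when study-wide follow-up ends", and adds: "Date of diagnosis for progression, first subsequent therapy and survival shall be reported". Protocol 5.3 and another paragraph of 8.2 say much the same. None of them makes an exception for new therapy.

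Protocol 10.7 ends RFS at the "time of first documented recurrence (after radical cystectomy) or death, whichever occurs first". For patients without an event, SAP 7.7.4 says: "If patients do not have recurrence tumor or death event then they are censored at the last RECIST assessment date". SAP 7.7 runs RFS on the safety population, so patients who never have cystectomy are included. For OS, SAP 7.7.5 censors at the date last known alive. Neither document says how RFS treats a new anticancer therapy that starts before recurrence, and no sensitivity analysis is planned.

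**The concern.** Two sites could each comply with the protocol and produce different RFS data for the same kind of patient. Anticancer therapy is allowed during follow-up (Protocol 7.4.2) and its date is collected, so such patients are foreseen. Those at issue start new therapy before an RFS event, for example as adjuvant treatment or as other treatment without cystectomy.

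If imaging ends there, the SAP rule treats these patients according to what happens next. One who dies stays at risk until death and has an event. One who stays well leaves the risk set at the last scan before the new therapy. A recurrence that is not imaged is either missed or dated only by the death that follows.

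Two-year RFS is a stated secondary objective. It is compared between cohorts by log-rank test and feeds the marker analyses. With 12 and 24 patients, one patient is 1/12 = 8.3 or 1/24 = 4.2 percentage points of a simple proportion. Scans that are never recorded may not be recoverable at analysis.

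**Working it through.** **No plan figure to reproduce.** The documents give no expected RFS rate, event count, power or rate of new therapy. For scale only, the plan's largest 90% exact interval widths for a proportion (Protocol 13.2.1.1: 0.51 and 0.36) do reproduce, at 0.509 for n = 12 and 0.361 for n = 24.

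**Mechanism.** Suppose two patients start new therapy at month 5, with their last scan then. One dies at month 20: at risk to month 20, event. The other is well at month 26: censored at month 5. After month 5, the only patients on new therapy left in the risk set are those who will die before cutoff.

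In large samples, let q be the share in the new-therapy group, τ the last scan and C the cutoff. Let S_N and S_O be RFS in the new-therapy group and in the others, and f_O the event density in the others. Let D(t) be the probability of death by t among new-therapy patients recurrence-free at τ, with density d(t). After τ:

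- at risk: R(t) = (1-q)·S_O(t) + q·S_N(τ)·[D(C) - D(t)]
- events: e(t) = (1-q)·f_O(t) + q·S_N(τ)·d(t)
- estimate at 24 months = exp(-∫ e/R), with the usual hazard before τ
- true value at 24 months = q·S_N(24) + (1-q)·S_O(24)

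**First set of scenarios.** All of the following are assumptions: exponential recurrence; last scan and new therapy at month 5; no later scans; median 9, 12 or 18 months from recurrence to death; cutoff at month 26.5. Case (a) borrows the background rates in Protocol 1.1, a 5-year RFS of 68% overall and 35% if node-positive. Converted to two years these are 0.68^(2/5) = 85.7% and 0.35^(2/5) = 65.7%. Case (b) assumes 80% and 40% at two years. A simulation of 400,000 patients per scenario and the formula agree to within 0.2 points.

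| Share in new-therapy group | (a) full imaging | (a) deaths only | (b) full imaging | (b) deaths only |
|---|---|---|---|---|
| 10% | 83.7-83.8% | 84.1-84.5% | about 76% | 76.9-77.9% |
| 20% | 81.6-81.7% | 82.1-83.1% | 72% | 73.8-75.2% |
| 30% | 79.7% | 80.0-81.5% | 68% | 70.2-72.6% |
| 40% | 77.6-77.8% | 77.2-79.7% | 64% | 66.2-69.5% |

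The extremes are 77.2 - 77.6 = -0.4 points and 69.5 - 64.0 = +5.5 points.

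**Second set.** Assumptions: new therapy at month 4, last scan at month 3, mean 12 months from recurrence to death, 30 months of follow-up, only later deaths captured.

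- 30% on new therapy, two-year RFS 40% against 75%: true 64.4%, estimate 65.9% (+1.5).
- 40% on new therapy, same risks: true 60.9%, estimate 62.3% (+1.4).
- 30% on new therapy, equal risk of 65%: true 65.1%, estimate 61.5% (-3.6).

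**Why the sign changes.** Removing survivors early inflates the hazard and pulls RFS down. Missing or late-dated recurrences push it up. Which effect dominates depends on how much worse the new-therapy group does and how soon death follows recurrence.

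**If footnote 18 is followed.** With scans every 3-6 months after new therapy, the estimate equals the truth (64.5% against 64.5%).

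**The case against.** The strongest reply is that the protocol already secures the data. Footnote 16 says imaging is not required; it does not forbid it. Footnote 18 and Protocol 5.3 and 8.2 keep two years of radiographic follow-up and ask for the progression date. Read together, a site may well go on scanning, and then nothing is lost. This stands as far as it goes: bias is a risk, not a certainty. It does not remove the conflict, because a site that relies on footnote 16 also complies.

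A reader might infer three stronger things that the documents do not support.

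- **That the stop applies to most patients, because finishing two doses counts as coming off treatment.** The item in Protocol 8.3 is "Completion of all study therapy and follow-up", which also needs completed follow-up. The lead-in to footnote 16 can be read as meaning early discontinuation only.
- **That salvage therapy after recurrence biases RFS.** Once a post-cystectomy recurrence is documented the RFS event has occurred, and later therapy cannot censor it.
- **That the error could be much larger, for example 72% against a true 64%.** That result censors every such patient when imaging stops, including those who later die, but the plan counts deaths. A downward result of 61% assumes that every later recurrence is found while no event-free patient has a later scan, which is hard to credit.

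It is also fair that RFS is unpowered and that the cohorts are small, sequential and not randomised. Any shift of this size is well inside the sampling error. That limits the importance of the point, but it is no reason to keep an avoidable source of bias.

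**Conclusion.** The point holds as a conflict between instructions together with a missing analysis rule. Where footnote 16 is followed for a patient who starts new therapy before a countable recurrence, SAP 7.7.4 makes censoring depend on later outcome.

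The size cannot be taken from the documents. In the scenarios run with only later deaths captured, two-year RFS moves by roughly -4 to +5.5 points, mostly upward when the treated group is at higher risk. The result rests on an assumed 10-40% in the new-therapy group, no scans afterwards, and the assumed risks and times to death. The range illustrates and does not bound the error: the equal-risk case was taken at 30% uptake, and its downward shift grows with uptake.

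The documents do not support saying that two-year RFS is biased, only that it may be. The primary safety endpoint and the sample size are untouched. The change is worth making because it is cheap and must be in place before follow-up data are lost.

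**What to change.** 1. **Protocol footnote 16, footnote 18 and 8.2, and the SAP Appendix I copy.** Reconcile them so that scans already done as standard of care continue to be recorded after new therapy. Recording should run until recurrence, progression (including in patients without cystectomy), death, or 2 years from registration. The limit must name progression without cystectomy, because Protocol 10.7 counts recurrence only after cystectomy and such a patient might otherwise never reach a stopping point.
2. **SAP 7.7.4.** State that recurrence or death counts regardless of new therapy, and that event-free patients are censored at their last scan, including scans after new therapy. State also whether progression without cystectomy is itself an RFS event; if it is not, the same asymmetry remains for those patients.
3. **One sensitivity analysis.** Treat new therapy started before recurrence as an event. Keep it as a sensitivity analysis only, because it answers a different question. In case (a) with 20% in the new-therapy group and a 12-month median to death, it gives 68.5% where full imaging gives about 82%.

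The cost is protocol and SAP wording plus some added eCRF entries for patients on later therapy. No procedure is added.
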